Carotid IMT QC: (i) Accreditation – after training by the Carotid IMT reading centre at Imperial College London, each sonographer will be asked to submit five accreditation scans to demonstrate understanding and adherence to the carotid IMT protocol (these can be performed on healthy volunteers); (ii) Reproducibility – sonographers will also be asked to perform a repeat baseline carotid IMT measurement on six of the first willing study participants on a second occasion. This can be performed at visit 1 or within a week of visit 1. Sonographers will be expected to demonstrate an intra-operator coefficient variation (CV) of <10% in these 6 individuals; (iii) On-going QC – sonographers will invite the same study participants to continue to undergo repeat carotid IMT measurements at visits 8, 12 and 16 in order to assess for any measurement drift. Results of Quality Control (QC) will be fed back to centres on a regular basis with follow up re-training/ certification as necessary.

HbA1c will be measured in accredited local laboratories participating in DCCT-aligned quality control programmes.

Lipids: samples of 7 ml EDTA plasma will be collected at Baseline, 0, 12, 24 and 36 months for centralised total cholesterol, HDL-cholesterol, direct LDL-cholesterol and triglycerides assay – participants will be asked to fast from midnight for all of these samples except Baseline (Visit R1). Aliquots will be stored at -80°C for transport to the laboratory in Glasgow for central assay. Total and HDL cholesterol and triglycerides will also be measured as per routine care in local routine laboratories to guide the requirement for and optimisation of statin therapy: the most recent values (within three months) will be recorded on Case Report Forms at the time of annual visits.

Microalbuminuria: status (positive or negative - see Appendix 5) as per routine care screening systems in local centres will be recorded annually in CRFs. At the same visits, aliquots of urine will be frozen and stored at -80°C (for later shipment to Glasgow) in case later centralised analysis is indicated.

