9. TIMELINE FOR PARTICIPANT IN STUDY

10. CLINICAL MEASUREMENTS AND EXAMINATIONS AT EACH VISIT

Prescreening visit. Provision of Patient Information Sheet and Expression of Interest form. Request for permission to contact.

Screening Visit (R1 start of Run-in Period) – non-fasting: Informed consent requested: if provided, full medical history, vital signs, weight, waist circumference, height measurements. Dispense study medication (which will be commenced following telephone prompting at visit R4). Give out diary. Treatment satisfaction questionnaire. Hypoglycaemia questionnaire. Titrate insulin. Blood samples (U&E, LFT, HbA1C, local laboratory total cholesterol, HDL and triglycerides, FBC, vitamin B12, C-peptide, microalbuminuria status. Samples for LDL, plasma biomarkers. Urine aliquot. Pregnancy testing if appropriate. Concomitant medications recorded. Review requirement for statin or ACE inhibitor against local practice, national guidelines and standard-of-care.

Telephone visits (R2-R4): insulin dose titration. Questions on adverse events. Visit R4 only: commence study medication.

Study Visit 1 (randomization): Vital signs, weight, waist circumference. Carotid IMT (can be done during last four weeks of Run-In). Retinal imaging. Endothelial function. Collect/ count unused medication. Dispense study medication with advice on dose titration. Give out diary. Hypoglycaemia questionnaire. Treatment satisfaction

questionnaire. Insulin dose titration/ record insulin dose. Blood samples (U&E, LFT, HbA1C, local laboratory total cholesterol, HDL and triglycerides, FBC, vitamin B12, microalbuminuria status if not available from Screening visit R1). Samples for LDL, plasma biomarkers. Lactate. Urine aliquot. Pregnancy testing if appropriate. Concomitant medications recorded. Questions on adverse events. Randomisation.

Telephone Visits 2-4 (0–1 month). Insulin dose titration/ record insulin dose, study medication dose titration (except at telephone visit 4). Questions on adverse events. Concomitant medications and Hypoglycaemia questionnaire (visit 4 only).

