1.6.2. GENERAL PRINCIPLES

All study data will be summarised as a whole and by treatment group at each study assessment point. Continuous variables will be summarised by the number of observations, number of missing values, mean, standard deviation (SD), median, quartiles and range. Categorical variables will be summarised by the number of observations, number of missing values and the number and percentage of individuals in each category.

Baseline data will be extracted from the Treatment Visit 1 electronic case report form (eCRF) page where possible; if values are missing, then data from the first screening visit (Run-in Visit 1) will be used.

The primary analysis, and all secondary analyses, will be carried out using all randomised individuals who provide sufficient data to conduct the particular analysis, regardless of their adherence to study protocol. For the primary outcome, a sensitivity analysis will be carried out using a Per-Protocol dataset, consisting of those individuals that completed the study according to protocol.

Graphical presentations will be specified and provided according to the results of the final analysis.

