All continuous secondary and tertiary outcomes will be summarised, overall and by treatment group at each time point; change from baseline will also be summarised. Non-Normally distributed variables will be transformed first. Repeated measures models will be applied to all continuous secondary and tertiary outcomes (except for the tertiary outcome “Progression of averaged maximal distal common carotid artery IMT” which will be analysed as per the primary outcome, using the maximal far wall IMT measurements as the main analysis, calculated as detailed below), assuming a general residual covariance structure, with the change from baseline as the outcome, and predictor variables of treatment, visit number (included as a class variable) and the outcome baseline level where available. The main analyses will test the significance of and provide an estimate of the main effect of treatment in this model. The treatment effect estimate, corresponding 95% confidence interval and p-value will be reported.

As an exploratory analysis to investigate whether the treatment effect varies over time, a visit by treatment interaction term will be added to each model and tested for significance. The p-value for the interaction term will be reported. In addition, the treatment effect, 95% confidence interval and p-value will be reported for each visit.

The main analysis of the averaged maximal distal IMT of the common carotid artery will use solely the maximum far wall cIMT measurements, and unlike the main analysis of the primary outcome, will not restrict to values < 1.5mm. A sensitivity analysis will also be performed using both the maximum near wall and the maximum far wall measurements as detailed in section 2.4.3.

The calculation of the averaged maximal distal IMT at each time point will use the following hierarchy:

1. Use all available data for the maximum far wall IMT regardless of data availability at other time points.

2. In instances where any duplicate angles are included (resulting in more than six angles per time point), average these duplicate angles first to result in one single measurement per angle.
3. Average next the angles within each side to result in one single measurement for each of the left and right sides
4. Average the remaining left and right measurements to obtain one result per time point

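### HbA1c, LDL, weight and eGFR are measured twice before randomisation but the secondary models adjust for one value only: valid, yet less precise than the collected data allow

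*SAP*

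**What the plan says.** **Two pre-randomisation values are collected.** The Schedule of Assessments (Protocol section 2) marks weight, the local U&E/HbA1c panel, the central LDL sample and the treatment satisfaction questionnaire at both R1 and Visit 1. Protocol section 10 agrees. R1 includes "full medical history, vital signs, weight, waist circumference, height measurements" and "Blood samples (U&E, LFT, HbA1C, local laboratory total cholesterol, HDL and triglycerides, FBC, vitamin B12, C-peptide, microalbuminuria status". Visit 1 repeats weight and takes "Blood samples (U&E, LFT, HbA1C, local laboratory total cholesterol, HDL and triglycerides, FBC, vitamin B12, microalbuminuria status if not available from Screening visit R1". The closing condition in that Visit 1 list belongs to microalbuminuria alone: the Schedule brackets only that item at Visit 1 and marks the U&E/HbA1c panel without brackets. For lipids, Protocol 6(b) says "samples of 7 ml EDTA plasma will be collected at Baseline, 0, 12, 24 and 36 months", where the first time point is R1 and is the only one not taken fasting.

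**One value is used.** SAP 1.6.2 takes baseline from Visit 1 where possible; "if values are missing, then data from the first screening visit (Run-in Visit 1) will be used". SAP 2.4.2 fits repeated measures models "with the change from baseline as the outcome, and predictor variables of treatment, visit number (included as a class variable) and the outcome baseline level", and adds: "The main analyses will test the significance of and provide an estimate of the main effect of treatment in this model". Neither document uses R1 as a second covariate, as part of an average or as an extra repeated measure.

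**The concern.** A single baseline value carries assay error and short-term within-person variation. A second pre-randomisation value of the same outcome will usually predict follow-up over and above the first. Leaving it out leaves removable variance in the residual. Protocol section 15 justifies covariate adjustment of the primary outcome on exactly this ground, to reduce residual variation and gain power, but the secondary models do not carry the idea as far as the data permit.

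HbA1c, LDL, weight and eGFR are four of the eight outcomes in the SAP's secondary list. They feed the rule that significant improvement in two or more counts as clinically meaningful, so the width of their confidence intervals matters.

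The fallback raises a lesser question. R1 precedes the run-in insulin optimisation, so a participant whose baseline is R1 contributes a value from a different clinical state.

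**Working it through.** **1. The plan's own figure.** Protocol 6(d) claims 90% power at 5% for about 0.3 SD in continuous outcomes. Taking 5% as two-sided and 1:1 allocation, power = Phi(d x sqrt(n/2) - 1.96).
- n = 250 per arm: 0.3 x sqrt(125) = 3.354, power 91.8%.
- n = 200 per arm (the evaluable number): 0.3 x sqrt(100) = 3.000, power 85.1%. Here 90% power needs 3.2415 x sqrt(2/200) = 0.324 SD.

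The claim reproduces on all 500 randomised participants, and on 400 only after rounding. Secondary power is therefore adequate, without much to spare at 0.3 SD.

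**2. Follow-up times (Schedule).** HbA1c, weight and U&E: months 3, 6, 12, 18, 24, 30, 36 (seven). Central LDL: months 12, 24, 36 (three). R1 is at -0.25 years and Visit 1 at 0.

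**3. Model (assumed, because the documents give no correlations).** Unit variance; correlation between times s and t is a x exp(-lambda x |t - s|), with a from 0.6 to 0.9 and lambda from 0.1 to 0.4 per year. Let F be the follow-up values and B the baseline set. The residual covariance is S_FF - S_FB S_BB^-1 S_BF, and the GLS variance of a common treatment effect is proportional to 1/(1' V^-1 1), where V is that residual covariance. Compare B = {Visit 1} with B = {R1, Visit 1}.

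| a | lambda | 7 visits: one, two baselines | cut | 3 visits: one, two baselines | cut |
|---|---|---|---|---|---|
| 0.6 | 0.1 | 0.3226, 0.2574 | 20.2% | 0.4380, 0.3806 | 13.1% |
| 0.6 | 0.4 | 0.3241, 0.2959 | 8.7% | 0.4854, 0.4690 | 3.4% |
| 0.9 | 0.1 | 0.1691, 0.1400 | 17.2% | 0.2854, 0.2607 | 8.7% |
| 0.9 | 0.4 | 0.2499, 0.2387 | 4.5% | 0.4776, 0.4721 | 1.2% |

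Over an even grid of a and lambda the cut is about 4-21% (median about 12%) with seven visits and about 1-14% (median about 5%) with three.

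**4. A different structure.** A stable component plus a serial component plus noise, again with assumed shares, gives cuts of about 7-14% with seven visits and 4.5-10% with three.

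**5. Upper bound: no decay.** Variance = (1 + (r-1)rho)/r - p rho^2/(1 + (p-1)rho), for r follow-ups and p baselines. With rho = 0.6 and r = 3: p = 1 gives 0.7333 - 0.3600 = 0.3733; p = 2 gives 0.7333 - 0.4500 = 0.2833; cut 24%. For rho from 0.6 to 0.9 the cut is 24-35% with three visits and 30-41% with seven.

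**6. Lower end: R1 is a weaker predictor.** Scaling R1's correlations by an assumed 0.8 gives about 2-11% (median about 5%) with seven visits and 0.4-7% (median about 2.5%) with three. If R1 has no partial correlation with follow-up given Visit 1 (for example R1-Visit 1 at 0.6, Visit 1-follow-up at 0.7 and R1-follow-up at 0.6 x 0.7 = 0.42), the cut is 0%.

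**7. Effect on power.** New power = Phi(2.8016/sqrt(1 - cut) - 1.96) from a start of 80%.
- Cut 5%: 2.874 - 1.96 = 0.914, power 82.0%.
- Cut 11%: 2.970 - 1.96 = 1.010, power 84.4%.

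Confidence intervals narrow by 1 - sqrt(0.95) = 2.5% and 1 - sqrt(0.89) = 5.7%.

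**8. Why not average the two values.** Take three follow-ups, Visit 1-follow-up and follow-up-follow-up correlations of 0.7, R1-Visit 1 at 0.6 and R1-follow-up at 0.5. The variance of the follow-up mean is (1 + 2 x 0.7)/3 = 0.80.
- Visit 1 only: 0.80 - 0.49 = 0.31.
- Two covariates: 0.80 - (0.49 + 0.25 - 2 x 0.6 x 0.35)/(1 - 0.36) = 0.80 - 0.50 = 0.30 (3% lower).
- Average: 0.80 - 0.6^2/0.8 = 0.80 - 0.45 = 0.35 (13% higher).

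**The case against.** The strongest reply is that nothing in the plan is wrong. Taking the value nearest randomisation, with a pre-specified fallback, is a standard baseline definition, and almost any SAP could add one more prognostic covariate. That stands: this is unused efficiency, not an error.

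It also stands that R1 may be the poorer predictor. Insulin regimens are optimised and statin need is reviewed between the two visits (Protocol 7.3(d) and (h)). R1 lipids are non-fasting (6(b)). HbA1c at R1 is confined to the entry window, whose lower limit is not re-applied at Visit 1 (7.1, 7.3(f)). Some R1 values may come from a recent clinic visit (7.3(e)). The main grid in step 3 ignores all of this, so the lower figures in step 6 deserve equal weight.

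Two outcome-specific points hold as well. The seven-visit range is not established for eGFR: the Schedule lists U&E at seven follow-up visits, but Protocol 6(b) speaks of annual-review creatinine values being recorded and used for eGFR, which would mean three. LDL has little power to gain: at the prior effect of 0.46 SD cited in Protocol 6(d), 200 per arm already gives Phi(4.60 - 1.96) = 99.6%, so the benefit there is a slightly narrower interval.

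A reader might infer that substituting R1 for a missing Visit 1 value biases the change from baseline. The documents do not support this. The model includes the same baseline as a covariate, so regressing (Y - B) on treatment and B gives the same treatment estimate as regressing Y on treatment and B; only the coefficient of B shifts by one. R1 is also pre-randomisation, so any run-in change is balanced by design. Substitution only adds covariate noise, and Protocol section 2 requires Visit 1 assessments to be complete before randomisation, so it should be uncommon. No missing rate is given.

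**Conclusion.** The point holds as a modest, nearly free gain in precision. The schedule facts are certain; the size is not. Under the assumed correlations the variance cut is about 4-21% with seven visits and about 1-14% with three, falling towards zero if R1 adds little beyond Visit 1. A 5-11% cut moves 80% power to about 82-84%.

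A reader might take the 24-41% no-decay figures as the expected gain. They require R1 to predict month 36 as well as Visit 1 does, and the run-in changes in the protocol make that unlikely.

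Nor does the point reach every outcome. Insulin dose is first recorded at Visit 1. Retinal images and endothelial function have one pre-randomisation measurement. Albuminuria and vitamin B12 deficiency are analysed as time to event. The effect on the two-or-more rule cannot be computed from the documents.

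**What to change.** In SAP 2.4.2, keep Visit 1 as the reference for change and add the R1 value as a second baseline covariate, with its own coefficient and not averaged with Visit 1, for HbA1c, LDL, weight and eGFR. Do the same for treatment satisfaction if it is modelled as continuous. Vitamin B12 deficiency is unaffected. State how many eGFR follow-up values enter the model.

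In SAP 1.6.2, where a Visit 1 value is missing, impute it from R1 instead of carrying R1 over unchanged. This reduces noise; it does not correct a bias.

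The cost is SAP wording, settled before unblinding, and one degree of freedom per model among roughly 400 evaluable participants. No new data are needed and the estimand is unchanged. Where R1 adds little beyond Visit 1, its coefficient will be small and little is gained or lost.

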1.6.3. CURRENT PROTOCOL

The current version of the protocol at the time of writing is version 3.0, dated 9th November 2015 and the accompanying NHS GG&C R&D protocol filenote. Future amendments to the protocol will be reviewed for their impact on this SAP, which will be updated only if necessary. If no changes are required to this SAP following future amendments to the protocol, this will be documented as part of the Robertson Centre Change Impact Assessment processes.

1.6.4. DEVIATIONS TO THOSE SPECIFIED IN THE PROTOCOL

The biomarker sample assays will be received after the database lock and therefore are not covered by this SAP, but will be detailed in a future SAP.

1.6.5. ADDITIONAL ANALYSES TO THOSE SPECIFIED IN THE PROTOCOL

There are no planned additional analyses to those specified within the Protocol.

1.6.6. SOFTWARE

Analyses will be conducted using SAS for Windows v9.3 or higher, SPlus for Windows v8.1 and/or R for Windows v2.7.0 or higher.

2. ANALYSIS

2.1. STUDY POPULATIONS AND ANALYSIS SETS

The Screened population will consist of all subjects screened for inclusion into the study.

The Intention To Treat (ITT) population will consist of all subjects randomised, regardless of subsequent participation in the study.

The modified-ITT (mITT) analysis set will include all subjects from the ITT population with data as available (without imputation) for analysis for each individual outcome.

The Per Protocol (PP) population will consist of all members of the ITT population with no major protocol deviations (met inclusion and exclusion criteria and no prohibited medications at randomisation), and who have cIMT available at treatment visits 1, 8, 12 and 16. All identified protocol deviations will be reviewed prior to unblinding the dataset, and classified as major or minor.

The Safety population will consist of all members of the ITT population who received at least one dose of study medication.

For any analyses to be carried out in multiple populations, if the populations are identical (e.g. if all members of the ITT population take at least one dose of study medication, then the ITT and Safety population are the same), then the analysis will only be reported once.

2.2. SUBJECT DISPOSITION

The number of patients in the Screened populations will be reported, as well as the number and percentage in the ITT Population. The reasons for screening exclusion will also be reported.

For those in the ITT population, the number and percentage in each treatment group will be reported.

For those in the ITT population, as a whole and by treatment group, the numbers and percentages in the Safety and PP populations will be reported.

Reasons for exclusion for populations will be summarised overall and by treatment group.

The number of subjects in the ITT population who completed or withdrew will be summarised, overall and by treatment group, along with the reasons for and time to withdrawal.

A by subject listing of all withdrawals from study after randomisation, and the reasons for withdrawal, will be provided.

Eligibility criteria and protocol deviations will also be summarised for the ITT population, overall and by treatment group.

A by subject listing of all protocol deviators will be provided.

2.3. BASELINE CHARACTERISTICS

In the ITT population, as a whole and by treatment group, summaries will be provided of the following baseline characteristics as included in the eCRF:

- Age and sex;
- ethnicity;
- smoking and alcohol habits;
- SBP, DBP and heart rate;
- height, weight, BMI and waist circumference;
- time since diabetes diagnosis;
- medical history – macrovascular, microvascular and other;
- family medical history (CV disease and diabetes);
- insulin regimen, including pump therapy;
- concomitant medications – statins, ACE-inhibitors, ARBs, antiplatelet and beta-blockers;
- treatment satisfaction questionnaire;
- hypoglycaemic events – minor and major;
- blood tests – creatinine, eGFR, capillary glucose (3-day average of each of: before breakfast, before mid-day meal, before evening meal and before bed) and C-peptide;
- average mean far wall cIMT (mm) of the common carotid artery;
- Lipid Assays – LDL cholesterol, HDL cholesterol, Total cholesterol and Triglycerides.

2.4. STUDY OUTCOMES

2.4.1. PRIMARY OUTCOME

The primary outcome will be the rate of progression of average mean far wall cIMT of the common carotid artery over the course of the study (36 months). In the mITT analysis set, as a whole and by treatment group, summary statistics for cIMT and change from baseline will be provided at baseline, 12, 24 and 36 months. The treatment effect estimate, 95% confidence interval (CI) and p-value will be estimated from a repeated measures regression model, with random intercept and random slopes, with cIMT as the outcome, and predictor variables of treatment, baseline cIMT and time. Time will be measured in years from baseline. A time by treatment interaction term will be included in the model, allowing different slopes for the two treatment groups. Adjustments for baseline covariates age, sex, smoking status, systolic blood pressure, BMI, HbA1c and LDL cholesterol will also be included as fixed effects.

A sensitivity analysis will also be carried out extending the model noted above to further adjust for the ultrasound probe frequency used.

Initial analyses will only include the measurements recorded with values < 1.5mm, in line with the Mannheim consensus, but the analyses will be duplicated to include all measurements regardless of value as a sensitivity analysis (see section 2.4.3).

Average mean far wall cIMT of the common carotid artery will be calculated as the average of the left and right mean measurements at each time point, using the following hierarchy:

1. Use all available data for the mean far wall IMT regardless of data availability at other time points.
2. In instances where any duplicate angles are included (resulting in more than six angles per time point), average these duplicate angles first to result in one single measurement per angle.
3. Average next the angles within each side to result in one single measurement for each of the left and right sides
4. Average the remaining left and right measurements to obtain one result per time point

No imputation of the primary outcome will be performed for the main analysis (the model described above will make use of all analysable data available for a subject). However, if any baseline covariates included as adjustments in the model (systolic blood pressure, BMI, HbA1c and LDL cholesterol) have neither treatment visit 1 data, nor run-in visit 1 data available, multiple imputation will be used, using the other baseline covariates included as adjustments with complete data at baseline (including age, sex and smoking status).

The analysis will be repeated for the PP population.

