We intend to analyse IMT data using repeated measures regression analysis assuming a linear progression in IMT measurements. We expect a mean progression of 0.044mm over 3 years (in the control arm) and a standard deviation (SD) for progression of 0.05 mm; therefore a final sample size of 200 per treatment arm will provide 90% power (at 5% significance level) to detect a difference of at least one third of an SD (0.0167mm) in 3 year progression of averaged mean cIMT between treatment arms - an effect size more conservative than reported for acarbose, statins, and TZDs on cIMT.

We therefore aim to recruit 500 patients (allowing for around 20-25% treatment discontinuation/ drop-out) and making the very conservative assumption that all those discontinuing treatment/ and withdrawing consent would not even have one follow up measurement (in reality this may occur after one or more follow up cIMT measurements so power will be more than this estimate).

Rates of progression and variation of common carotid artery IMT vary widely between different studies and data from T1DM patients, other than the patients in DCCT/EDIC who are younger than this trial participants, are sparse. Our estimate of progression rate over three years (0.044 mm) is at the lower boundary of that reported by Bots in a meta-analysis of cIMT progression rates of control groups (almost all non-diabetic) from published RCTs.⁵⁰ In that analysis the annual rate of change in mean cIMT was 0.0176 mm (95% CI, 0.0149 to 0.0203). Whilst many of the control group participants in this pooled analysis were not on statins (in contrast to many REMOVAL participants with T1DM) almost all were non-diabetic so that their progression rate would be expected to be lower than in diabetes.

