14. CRF REPORTING AND DATA COLLECTION

14.1 Randomisation

A central randomisation facility based at the Robertson Centre for Biostatistics, University of Glasgow will be contacted either by telephone or by a web-based service and randomised therapy will be assigned. Randomisation will be stratified by study site and based on randomly permuted blocks allocated within each trial centre.

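### Randomisation is stratified by site but no SAP model contains site; if sites differ in measured cIMT progression, the primary confidence interval is somewhat conservative, though not biased

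*SAP*

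**What the plan says.** Protocol 14.1 is explicit: "Randomisation will be stratified by study site and based on randomly permuted blocks allocated within each trial centre". The block size is not given. Protocol 6(g) counts 18 sites, with five UK sites in reserve.

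SAP 2.4.1 models cIMT with a random intercept and random slope per participant, and with treatment, baseline cIMT, time and treatment by time as predictors. It then lists the covariates: "Adjustments for baseline covariates age, sex, smoking status, systolic blood pressure, BMI, HbA1c and LDL cholesterol will also be included as fixed effects". Site is not among them. The nearest term is ultrasound probe frequency, which appears only in a sensitivity analysis.

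For continuous secondary outcomes, SAP 2.4.2 uses change from baseline with "predictor variables of treatment, visit number (included as a class variable) and the outcome baseline level where available". Site is also absent from the negative binomial, Cox and logistic models in SAP 2.4.2, from the sensitivity and subgroup analyses in 2.4.3 and 2.4.4, and from the ANCOVAs in 2.4.5.5 and 2.4.5.6. The SAP gives no reason for leaving it out.

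Protocol 6(b) limits each site to at most two sonographers and allows equipment to be checked through the site's own annual service. It also schedules repeat scans at visits 8, 12 and 16 "in order to assess for any measurement drift".

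**The concern.** Permuted blocks within site balance site effects between the arms, which lowers the true sampling variance of the treatment contrast. A model without the strata does not take credit for that. It still charges between-site variance to the reported standard error, so the test rejects less often than 5% under the null and the interval covers more than 95%.

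Site differences in measured progression are plausible here. The operators are site-specific, servicing can be local, and probe frequency varies enough for the SAP to plan an analysis of it. Several secondary outcomes also depend on local laboratories or local practice: HbA1c, creatinine for eGFR, and insulin adjustment.

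What is at stake is precision. Protocol 15 says that covariates are adjusted for in order to reduce residual SD and gain power. Leaving out the one factor on which the randomisation was balanced works against that aim. Conservatism also bears on the secondary outcomes, because SAP 2.4.2 ties their interpretation to how many of them reach significance.

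**Working it through.** **Inputs from Protocol 6(d).** 200 analysed per arm, 5% significance (taken as two-sided), difference 0.0167 mm, and "standard deviation (SD) for progression of 0.05 mm".

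**Input not in the documents.** r, the share of the variance of 3-year progression that lies between sites. The range 0 to 0.20 is assumed.

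**1. The plan's own figure.** SE = 0.05 × √(2/200) = 0.00500 mm. Power = Φ(0.0167/0.00500 − 1.96) = Φ(1.38) = 0.916, against the stated 90%. The 95% half-width is 1.96 × 0.00500 = 0.00980 mm. The planned power reproduces.

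**2. Effect of omitting site.** With arms balanced within site, the true SE is 0.00500 × √(1−r), while the model without site reports about 0.00500. Hence:

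- interval width, without site relative to with site: 1/√(1−r)
- real type I error without site: 2 × [1 − Φ(1.96/√(1−r))]
- real power without site: Φ[(0.0167 − 0.00980)/(0.00500√(1−r))]
- power with site: Φ[0.0167/(0.00500√(1−r)) − 1.96]

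| r | Width ratio | Half-width with site (mm) | Type I error without site | Power without site | Power with site |
|---|---|---|---|---|---|
| 0 | 1.000 | 0.00980 | 5.0% | 91.6% | 91.6% |
| 0.05 | 1.026 | 0.00955 | 4.4% | 92.2% | 92.9% |
| 0.10 | 1.054 | 0.00930 | 3.9% | 92.7% | 94.1% |
| 0.20 | 1.118 | 0.00877 | 2.8% | 93.9% | 96.2% |

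**3. Simulation check.** These runs compared two-sample analyses of progression with and without site, using 400 participants, 18 or 23 sites and blocks of 4 (block size and site sizes are assumptions). Without site, type I error was 4.6-4.7% at r = 0.05, 3.7-4.3% at 0.10 and 2.5-3.5% at 0.20. With 23 sites the width ratios were 1.02, 1.05 and 1.11, and including site kept type I error near 5%. At r = 0, including site as a fixed effect widened the interval by about 0.3% (ratio 0.997).

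**4. Which site term matters.** The primary contrast is a difference in slopes. A small check fitted the SAP's random-intercept, random-slope model to three simulated data sets at r = 0.10 (20 equal sites, 400 participants, assumed reading error SD 0.02 mm). The SE of the 3-year treatment effect was 0.00610 mm without site, 0.00610 with a site main effect only, and 0.00577 with site by time: 0.006103/0.005769 = 1.058. A site level term alone recovers nothing, while site by time recovers what the formula predicts. Those fits used fixed site terms. When arms are balanced within site, treatment is orthogonal to site, so random site slopes give essentially the same variance for the contrast.

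**5. How far the 90% statement reaches.** It holds at 200 per arm. Protocol Appendix 6 accounts for 379 + 50 = 429 randomised. With 20% loss that would leave 429 × 0.8/2 = 171.6 per arm, an SE of 0.05 × √(2/171.6) = 0.00540 and power of 87.2% at r = 0. The same formulas at r = 0.10 then give 88.4% without site and 90.3% with it.

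**The case against.** The strongest reply is that the effect is small and depends on an unknown. A reader might infer that the interval is too wide as a matter of fact. The documents do not support that: they give no between-site variance, and at r = 0 nothing changes. The 20% case has no support in them either. Nor does the omission bias the estimate or inflate type I error. All of this stands.

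The protocol also limits r. Section 6(b) requires the same ultrasound system and presets throughout, phantom or service calibration, sonographer certification, and one central reader using semi-automated software under masked quality control. Keeping the same system may mean within each site over time, which the provision for local servicing suggests, but the text does not settle it. So separate machines at each site are implied rather than stated. Baseline cIMT and the random intercepts already absorb stable site differences in level. Only differences in progression, or drift, remain.

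A reader might also infer that quality control cannot detect site drift. That goes too far. Repeat scans by the same sonographer on the same participants do not by themselves separate operator drift from true progression. But phantom calibration, where used, checks the machine independently, and results are fed back with retraining. Drift common to both arms within a site is in any case balanced by the stratification.

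The argument should not be carried to every model. Protocol 6(d) expects 13.7% retinopathy progression, so at most about 0.137 × 400 = 55 events, or two to three per site over 18 to 23 sites. In a simulation with assumed site sizes, fixed site effects left four to six sites without events and raised the SE of the log odds ratio by 2-4%. For the continuous secondary outcomes, change from baseline adjusted for baseline removes constant laboratory offsets. A gain there is plausible but has not been sized.

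What survives is the omission itself, its direction, and the fact that correcting it costs almost nothing.

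**Conclusion.** The point holds as a modest efficiency improvement. Site is the stratification factor and is in no SAP model. If sites differ in measured cIMT progression, the variance falls into the between-subject slope variance, not the within-subject residual, and the treatment-by-time estimate is unbiased with a conservative interval.

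The width penalty is nil at r = 0, about 2.6% at 0.05, about 5% at 0.10 and 11-12% at 0.20. The gain in real power is about 1 point at r = 0.05 to 0.10. The values of r are assumed, and the formula treats the arms as balanced within every site. The validity of the primary test is not in question.

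**What to change.** Before unblinding, amend the SAP as follows.

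- **2.4.1, primary cIMT model:** add a random site intercept and a random site slope on time. Specify this one form rather than leaving a choice between fixed and random effects, and say what will be done if the site variance is estimated at zero or the model does not converge. A site main effect alone is not enough.
- **2.4.2, repeated-measures models for continuous secondary outcomes:** add site as a random effect. The outcome there is already change from baseline, so a single site term captures site differences in change.
- **Retinopathy logistic model and Cox models:** do not add fixed site effects to the former, and do not require stratification by site in the latter.
- **Sensitivity analysis:** keep the current primary model, without site.

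The cost is SAP wording and programming of the added terms, with no new data. If sites do not differ at all, the simulated SE rises by less than 0.5%.
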